3. Willing to give informed consent
4. Newborns without any symptoms and complaint

Predefined exclusion criteria will be:

1. Newborns with obvious congenital abnormalities (with clear medical consequences)
2. Newborns with needs for intensive care treatment
3. Newborns with low (2499g or less)
4. Newborns with confirmed non-type 2a hips

Randomization sequence will be created using Excel 2007 (Microsoft, Redmond, WA, USA) with a 1:1 allocation using random block sizes of 4 by an independent researcher with no clinical involvement in the trial. After obtaining the consent from the parents, details of the allocated group will be given on colored cards contained in sequentially numbered and sealed envelopes. These will be prepared by the principal investigator and kept in an agreed location on the post-delivery ward. Randomization will take place before discharge when the data collector/neonatologist gives detailed consultation on usual postnatal care of newborns. Corresponding envelopes will be opened

only after the enrolled newborns completed all baseline assessments and it is time to allocate the intervention. Whereas parents allocated to the swaddling group and the research assistants will be aware of the allocated arm, the outcome assessor/radiologist will be kept blinded to the allocation.

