3. Analysis of the 7-days prospective mother's diaries used for sleeping and crying/fussing outcome measure: as mother's own reported behaviour during 2 time periods
4. Unscheduled visits from a monitoring research assistants: in order to estimate unreported non-compliance conducted for all families 1 to 3 times
5. End-study research assistant impressions' questionnaire: of their impression about compliance in each family and the consistency and extent of accuracy of the reports from each family during each week of child's life

For analysis, the first and third methods of exposure recordings above will be quantifiable and will be combined to reveal exposure to swaddling per child for use in per-protocol analysis. The other three methods detailed above will be triangulated with the data from the diaries.

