3.4. Outcome assessments

The primary outcome of the study will be the number of “non-Type 1” hip cases at the any monthly follow-up ultrasound control visits.

The secondary outcomes are:

- a. number of DDH cases (Graf Type 2a-, Type C, D and Type 4) at any monthly follow-up ultrasound control visits
- b. correlation between the primary outcome and the swaddling frequency (in hours) per day and swaddling duration in days
- c. primary and secondary outcomes association with the swaddling.

Operational definitions

Swaddled: Newborns are swaddled in the common traditional Mongolian method at least 20 hours per day for 4-6 weeks

Non swaddled: Newborns are not swaddled at all.

The “non-Type 1” hip case: a neonate who’s Graf ultrasound type is other than Type 1 at any monthly follow-up visits

Physiologically immature or Graf Type 2a hip: has a certain degree of physiological delay in ossification of the bony acetabular roof. The alpha angle is between 50 and 59, the beta angle is between 55 and 77, and the patient is younger than 6 weeks of age.

Graf Types 2a- and 2a+: Starting from 55° alpha at 6 weeks of age and assuming a spontaneous maturation of 1° per week. Type 2a+ is still considered to be physiological while 2a- hips are assigned to the group of DDH.

Swaddling hours: according to the 24-hour diaries of swaddling and non-swaddling patterns of mothers and research assistants' compliance check reports

Swaddling days: according to the 24-hour diaries of swaddling and non-swaddling patterns of mothers and research assistants' compliance check reports

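### An unblinded end-of-study rating of each family's compliance and truthfulness is cross-checked against the swaddling diaries after hip results exist, so measured exposure could come to depend on the outcome

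*Protocol*

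**What the plan says.** Protocol section 3.3 (Monitoring) names five sources: (1) a 24-hour recall taken at each weekly home visit, (2) direct observation at those visits, (3) mothers' 7-day prospective diaries, (4) unscheduled visits, and (5) an "End-study research assistant impressions' questionnaire". Source 5 records assistants' views "of their impression about compliance in each family and the consistency and extent of accuracy of the reports from each family", by week of the child's life.

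On use, section 3.3 says that "the first and third methods of exposure recordings above will be quantifiable and will be combined to reveal exposure to swaddling per child", for the per-protocol analysis, and then that "The other three methods detailed above will be triangulated with the data from the diaries".

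On blinding, section 3.2 says that "the research assistants will be aware of the allocated arm, the outcome assessor/radiologist will be kept blinded to the allocation".

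Section 3.4 (Operational definitions) bases swaddling hours, and in the same words swaddling days, on the diaries together with the assistants' compliance check reports. Section 3.5 correlates both measures with non-Type 1 status by Pearson's coefficient, and evaluates outcomes by intention to treat.

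**The concern.** An exposure measure should be complete before anyone who shapes it can know the outcome. Source 5 asks staff who know the arm to judge, at the end, whose reports were accurate. Section 6 states the team's hypothesis that swaddling harms Type 2a hips, and section 3.3 expects some non-swaddling families not to adhere.

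A poor hip in a non-swaddling family could then prompt doubt about its diary, and so could a good hip in a swaddling family. If that doubt changes the exposure value, or who counts as compliant, the per-protocol result and the correlation of swaddling hours and days with non-Type 1 hips (secondary outcome b) move towards the hypothesis even if swaddling has no effect. The form also asks for week-by-week recall after those weeks have passed.

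**Working it through.** The plan gives no figure on this point, so there is none to reproduce. The check is of timing and use, followed by two illustrations of size.

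**Timing and use**

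| Step | What the Protocol fixes |
|---|---|
| Exposure period | 4-6 weeks from birth (3.1) |
| Home visits | Weekly, until 4-6 weeks of age (3.3) |
| First follow-up scan | At 4-6 weeks, then monthly until Type 1 (3.3) |
| Visible sign of outcome | Orthosis for Type 2a-, 2c or worse (3.3) |
| Source 5 rating | End of study, with no date (3.3) |
| Assistants' knowledge of arm | Known (3.2) |
| Assistants' knowledge of hip result | Neither given nor withheld in the text |
| Use of the rating | Triangulated with the diaries, with no rule for disagreement (3.3) |

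On an ordinary reading of end of study, the rating follows at least the first outcome scan.

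**Illustration 1: arm comparison among families judged reliable**

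Assume no true effect, with a proportion p = 0.25 of non-Type 1 hips in both arms. This is an assumption; it lies midway between the planning values of 10% and 40%. Take 32 infants per arm, which is the planned 40 less 20% dropout: 40 × 0.80 = 32. Call a family discordant if it has a non-Type 1 hip without swaddling or a Type 1 hip with swaddling. Suppose a share q of discordant families is judged unreliable and set aside.

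- Non-swaddled rate = p(1−q) / [p(1−q) + (1−p)]
- Swaddled rate = p / [p + (1−p)(1−q)]
- q = 0.10: 0.225/0.975 = 23.1% against 0.25/0.925 = 27.0%, a difference of 4.0 points
- q = 0.25: 0.1875/0.9375 = 20.0% against 0.25/0.8125 = 30.8%, a difference of 10.8 points

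The expected number of discordant families is 32 × 0.25 + 32 × 0.75 = 32. So q = 0.10 sets aside about 3 families in all, and q = 0.25 about 8.

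Simulated Pearson chi-square tests at a nominal 5% reject in about 5% of trials with q = 0, about 7% with q = 0.10 and about 16% with q = 0.25.

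**Illustration 2: secondary outcome b**

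Take the swaddling arm only and assume 40% non-Type 1, daily hours roughly Normal with mean 18 and SD 4 (capped at 24), and no true dose effect. Suppose recorded hours are raised in half of the non-Type 1 infants (5,000 simulated trials per setting).

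| Hours added | Mean r, n = 32 | False-positive rate, n = 32 | Mean r, n = 40 | False-positive rate, n = 40 |
|---|---|---|---|---|
| 0 | 0.00 | 5% | 0.00 | 5% |
| 1 | 0.06 | 6% | 0.06 | 7% |
| 2 | 0.11 | 10% | 0.12 | 12% |
| 4 | 0.22 | 23% | 0.21 | 27% |

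The mean, SD, shift and share affected are all assumptions; the Protocol gives none of them.

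**The case against.** The case against is substantial, and much of it stands.

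- **Compliance is not judged only at the end.** Assistants observe the baby at every weekly visit, and unscheduled visits look for unreported non-compliance. Only the overall impression and the rating of report accuracy are left to the end. This stands.
- **The rating need not decide anything.** A reader might infer that source 5 has the last word on whose diary to believe. The text does not say so. The exposure number comes from sources 1 and 3, and triangulation is undefined. This stands: re-grading is permitted, not prescribed.
- **Section 3.4 does not name this form.** It would be tempting to read its compliance check reports as the end-of-study questionnaire. The phrase fits the visit checks at least as well, so it shows that assistants' reports enter the exposure definition but not that this rating does.
- **Knowledge of the result is inferred.** No document says that assistants are told hip results, and no assistant visit is scheduled after 4-6 weeks. The orthosis reveals only part of the primary outcome, because a Type 2a+ hip is non-Type 1 but is followed without treatment. This stands as a limit on certainty.
- **Scope is narrow.** The intention-to-treat analysis does not use measured exposure. Secondary outcome c is not clearly affected either, since Annex 4 Tables 2 and 3 compare control with intervention.
- **The illustrations assume outcome-driven discounting.** They show what would follow from it, not that it will happen.
- **Triangulation rules and data lock belong in a SAP.** This is fair for the rules. It does not cover when the form is completed, which the Protocol itself fixes. If assistants have learned the hip result by then, no later analysis rule can make the rating blind to it.

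**Conclusion.** The point holds in a limited form. Unblinded assistants complete a subjective, retrospective rating at a time when hip results exist. Nothing shields them from those results, and nothing stops the rating from altering the exposure used in the per-protocol analysis and secondary outcome b. The primary intention-to-treat comparison is untouched.

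The size cannot be read from the Protocol. Under illustration 1, false positives rise from 5% to about 7% or 16% as 10% or 25% of discordant families are discounted. Illustration 2 gives about 10% to 12% for a 2-hour shift in half of the non-Type 1 infants. All of these figures rest on assumed rates of re-grading. They support a change worth making for the secondary analyses. They do not support a claim that the exposure data will be biased.

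**What to change.** In section 3.3:

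1. Complete the impression form at each weekly visit, or at the last planned home visit before the first follow-up scan, in place of end of study.
2. Derive exposure per child from sources 1 and 3, and word the definitions of swaddling hours and days in section 3.4 to match.
3. Close the per-child exposure file before any hip result reaches the research assistants, and do not change exposure after that.
4. Use any impressions recorded later only in a sensitivity analysis.

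The cost is wording and a dated file closure: the form already exists and the visits are already planned. The downside is that the form no longer covers anything learned after the last home visit; point 4 keeps a place for such information.

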3.4. Outcome assessments

The primary outcome of the study will be the number of “non-Type 1” hip cases at the any monthly follow-up ultrasound control visits.

The secondary outcomes are:

- a. number of DDH cases (Graf Type 2a-, Type C, D and Type 4) at any monthly follow-up ultrasound control visits
- b. correlation between the primary outcome and the swaddling frequency (in hours) per day and swaddling duration in days
- c. primary and secondary outcomes association with the swaddling.

Operational definitions

Swaddled: Newborns are swaddled in the common traditional Mongolian method at least 20 hours per day for 4-6 weeks

Non swaddled: Newborns are not swaddled at all.

The “non-Type 1” hip case: a neonate who’s Graf ultrasound type is other than Type 1 at any monthly follow-up visits

Physiologically immature or Graf Type 2a hip: has a certain degree of physiological delay in ossification of the bony acetabular roof. The alpha angle is between 50 and 59, the beta angle is between 55 and 77, and the patient is younger than 6 weeks of age.

Graf Types 2a- and 2a+: Starting from 55° alpha at 6 weeks of age and assuming a spontaneous maturation of 1° per week. Type 2a+ is still considered to be physiological while 2a- hips are assigned to the group of DDH.

Swaddling hours: according to the 24-hour diaries of swaddling and non-swaddling patterns of mothers and research assistants' compliance check reports

Swaddling days: according to the 24-hour diaries of swaddling and non-swaddling patterns of mothers and research assistants' compliance check reports

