In many cultures around the world newborn babies are swaddled to calm them down and fall asleep, and some cultures believe that swaddling can prevent the baby from suffering cold weather especially during winter time. In Mongolia, swaddling is an ancient practice and nowadays it still remains common child care in the first months of life. Mongolian traditional way of swaddling technique involves tight, prolonged wrapping from the head or neck down in two to three layers of thin cotton cloth, covered by layers of thick blankets and binding with 2-3 tiers. However, this prolonged swaddling in the first year of life did not have any significant impact on children's early mental or psychomotor development.²²

In Mongolia, the Graf's method of hip ultrasound was introduced in 2007 by Swiss-Mongolian Pediatric Project (SMOPP), a private/non-governmental humanitarian aid project, and has subsequently become step by step a nationwide screening program. Trained neonatologists or pediatricians of Maternity hospitals screen all newborns using the Graf's method²³ of hip ultrasound and perform a flexion-abduction treatment, if necessary. The routine guideline is the following: newborns with Type 1 hips are discharged without any further follow-up. Newborns with Type 2a hips are followed up by ultrasound in monthly intervals until these mature. Children who have 2a hips during the course of follow-up are either followed up (Type 2a+), or treated if the hip insufficiently matured (Type 2a-). Children with Type 2c to 4 hips are treated with a Tübingen hip extension and abduction orthosis and also followed up until fully mature. Children

with Type 4 hips that could not be splinted are referred for surgical interventions.²² Full documentations of all cases is mandatory.

Recent studies in Mongolia showed that 10-15% of newborns have physiological immaturity (Type 2a hip by Graf method) at birth.⁸ Given the high prevalence of traditional swaddling in the country, any association with DDH could have large public health implications. We will investigate the effect of traditional tight and prolonged swaddling on DDH in Mongolia in this prospective randomized controlled trial (RCT).

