2. OBJECTIVES

Mongolian traditional prolonged swaddling where arms and legs are extended and hips are in adduction position increases the risk for DDH. This hypothesis is going to be tested in this study.

The primary outcomes: The number of “non-Type 1” hip cases at the monthly follow-up ultrasound control visits

The secondary outcomes:

- a. number of DDH cases (Graf Type 2a-, Type C, D and Type 4) at any monthly follow-up ultrasound control visits and rim defects at 12 months’ follow-up
- b. correlation between the primary outcome and the swaddling frequency (in hours per day) and swaddling duration (in days)
- c. primary and secondary outcomes association with the swaddling.

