For babies assigned to the “swaddling” group, parents will be instructed to follow a pattern of traditional Mongolian swaddling as described above. For babies assigned to the “non-swaddling” group, parents will be instructed to do not swaddle at all and only use a wide sleeping bag with free leg position.

Trained research assistants will make home visits on weekly basis until the infants are 4-6 weeks of age to check and monitor the compliance of the families by observing the baby during every home visit and collecting retrospectively 24-hour diaries of swaddling and non-swaddling patterns. Also unscheduled visits from monitoring research assistants will be organized to estimate unreported non-compliance conducted for all families 2 to 3 times.

At 4-6 weeks follow up visit, the babies will be checked by Graf’s method of hip ultrasound performed by a trained radiologist uninformed about the initial status of the hips. Regardless of the study group, monthly controls will be fixed until complete maturation to Graf type 1 is documented. Families, who did not show up for follow-up will be contacted by phone or home

visit. In cases when the parents will not be able/willing to come to the follow-up control visit(s), the PI will visit the family and make the follow-up ultrasound examination at their home using a portable ultrasound device (MicroUs EXT-1H, REV:C). All infants in need of therapy (Graf type 2a-, 2c or worse) will be treated with Tubinger orthosis.

Monitoring: In the non-swaddling group, it is expected that some families would not adhere to their instructions of not swaddling because of grandparents/cultural pressures. To monitor compliance and obtain a measure of exposure, multiple sources of information will be used:

1. A retrospective 24-hour history of swaddling/clothing: will be recorded by research assistants during each weekly home visit through recording the carer's descriptions of the style of dress/clothing/ swaddling and length of each during the past 24-hour within the 24-hour retrospective diaries (a kind of behaviour diary adapted to record swaddling/clothing pattern)
2. Direct observation of research assistants during weekly visits: of the dressing/clothing/ swaddling of each child and discreetly recording observations of the type of baby clothing items that each family washed and hung to dry on the day of visit (available for observation during the majority of visits)

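### The DDH outcome list in Protocol sections 2 and 3.4 leaves out Graf Type 3, which the protocol's own treatment range includes

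*Protocol*

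**What the plan says.** **DDH list.** Section 3.4 gives secondary outcome (a) as the "number of DDH cases (Graf Type 2a-, Type C, D and Type 4) at any monthly follow-up ultrasound control visits". Section 2 has the same list and extends the item: "at any monthly follow-up ultrasound control visits and rim defects at 12 months". Annex 4, Tables 2 and 3, have a DDH row without a definition.

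**Treatment range.** Section 3.3: "All infants in need of therapy (Graf type 2a-, 2c or worse) will be treated with Tubinger orthosis". The Summary says the same. For the routine guideline, section 1 says: "Children with Type 2c to 4 hips are treated with a Tübingen hip extension and abduction orthosis".

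**Rim defects.** Section 2 includes them at 12 months. Annex 4 has a rim-defect row in Table 2, tied to follow-ups in general, and lists rim defect as a secondary outcome in Table 3 with no time point. Section 3.4 does not mention them.

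**Type 2a and its split.** Section 3.4 limits Type 2a to infants under 6 weeks with alpha between 50 and 59. It defines the 2a+/2a- split as "Starting from 55° alpha at 6 weeks of age and assuming a spontaneous maturation of 1° per week" and assigns 2a- to DDH. On the first follow-up scan, section 3.3 says "At 4-6 weeks follow up visit, the babies will be checked by" ultrasound, with monthly scans after that until Type 1 is documented.

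**The concern.** The outcome list is closed: it names four categories and has no catch-all. The treatment passages use an open or continuous range. The two do not cover the same hips, and the one left out of the outcome lies inside the range that the trial treats. Whoever codes the outcome must either follow the list and leave a treated infant out of the DDH count, or depart from the written definition. That choice should not be made after the data are seen, particularly for the condition named in the trial's title and hypothesis.

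The rim-defect and 2a- wording raises a lesser question of the same kind: which outcomes are in the set, at what time, and which rule gives an infant's DDH status at a given scan age.

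**Working it through.** The protocol states no figure for the DDH outcome. Its only design figure is for the primary outcome. It reproduces and does not depend on this point: 7.9 × (0.1×0.9 + 0.4×0.6) / 0.3² = 7.9 × 0.33 / 0.09 = 28.97, so 29 per group. The check is therefore a comparison of passages.

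**1. Coverage of each Graf category**

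| Category | DDH outcome (sections 2, 3.4) | Treated in the trial (Summary, 3.3) | Routine guideline (section 1) | Primary outcome, not Type 1 (3.4) |
|---|---|---|---|---|
| 2a- | yes | yes | yes | yes |
| 2c (printed as Type C) | yes | yes | yes | yes |
| D | yes | yes | yes | yes |
| 3 | **no** | yes | yes | yes |
| 4 | yes | yes | yes | yes |

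The protocol never names Type 3. Its place in the treated range follows from reading a range that runs from 2c to 4, or from 2c upward, as including it. On that reading it is the only category where the outcome and treatment columns disagree.

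**2. Who would be lost.** The outcome counts a qualifying type at any monthly visit. A Type 3 infant who is also read as 2a-, 2c, D or 4 at another visit is counted anyway. Only infants whose sole reading in the range is Type 3 drop out. All infants enter as Type 2a, and no rate of progression to Type 3 is given, so the number cannot be computed.

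**3. The 2a- rule by age.** Threshold = 55 + (age in weeks − 6):

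| Age (weeks) | 4 | 5 | 6 | 7 | 8 | 9 | 10 | 11 |
|---|---|---|---|---|---|---|---|---|
| Threshold (degrees) | none | none | 55 | 56 | 57 | 58 | 59 | 60 |

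Read together, the definitions do not meet. Before 6 weeks a hip can be Type 2a but has no +/- class; from 6 weeks it has a +/- class but no longer meets the age limit for Type 2a.

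Two illustrations, with growth rates that I have assumed:

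- *Steadily slow hip:* 50 degrees at birth, +0.75 per week. At week 4 it is 50 + 0.75×4 = 53.0, with no class. At week 8 it is 50 + 0.75×8 = 56.0, against a threshold of 57, so it is 2a-. It is found late, not lost.
- *Hip that catches up:* the same to week 6, then +1.75 per week. Scanned at weeks 6 and 10, it is 54.5 (2a-, a DDH case) and then 54.5 + 1.75×4 = 61.5 (Type 1). Scanned at weeks 4 and 8, it is 53.0 (no class) and then 54.5 + 1.75×2 = 58.0 (2a+), so it is never a case.

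Dependence on scan date is therefore possible, but it needs a hip that recovers between scans.

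**4. Rim defects.** Section 2 adds them after the DDH list and Table 3 gives them their own row. They are a separate outcome, so their absence from section 3.4 changes no infant's DDH status. It leaves the secondary outcomes and their timing inconsistent between sections.

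**The case against.** The strongest reply is that the Type 3 omission is clerical. The list is visibly garbled (Type C stands where 2c is meant), and the treatment range is complete in three other places. An analyst who knows the Graf system would probably count Type 3. That is plausible, but the same closed list stands in both outcome sections, and an outcome definition is applied as written. A separate analysis plan might define DDH fully; that would not remove the contradiction inside this protocol.

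On the 2a- rule, the reply is largely right. The threshold rises with age, infants not yet Type 1 are rescanned monthly, and most slow hips are therefore picked up later. What remains is narrow: section 1 allows 2a- to be called during follow-up with no lower age, while section 3.4 starts the split at 6 weeks.

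A reader might infer more than the documents support:

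- *That rim-defect wording or early scans cause DDH cases to be missed on any scale.* Rim defects are a separate outcome, and the missed 2a- case above rests on assumed growth.
- *That the comparison between arms is biased.* The scan window is the same in both arms, so the schedule alone does not imply this.
- *That one or two infants decide the DDH comparison.* No DDH event rate for this population is given. With 40 × 0.8 = 32 evaluable per arm, Fisher's exact test gives a two-sided p = 0.053 for 5 against 0 and p = 0.024 for 6 against 0. With 3 to 5 events in all, no split reaches 0.05; with 6, only 6 against 0 does.

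**Conclusion.** The point holds for Type 3. The written DDH outcome leaves out a category inside the range that the protocol treats, so an infant could be treated as dysplastic and not counted as DDH. This rests on reading the ranges from 2c to 4 and from 2c upward as containing Type 3.

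Its reach is limited. It concerns a secondary outcome; the primary outcome and the sample size do not change. The number of infants affected is unknown and may be zero. The rim-defect and 2a- points are alignment matters: the first is an inconsistency in the outcome set, the second an incomplete rule with possible but unquantified dependence on scan date.

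**What to change.** - Define the DDH outcome once, as Graf 2a-, 2c or worse, which is the protocol's own phrase. Use that definition in sections 2 and 3.4 and for the DDH rows of Annex 4. Reconcile the outcome list with the treatment passages in the Summary and sections 1 and 3.3.
- List rim defects in section 3.4 as a separate outcome with one time point, and make section 2 and Annex 4, Tables 2 and 3, agree with it.
- Reconcile three statements so that DDH status in the analysis follows one stated rule: the 2a+/2a- split from 6 weeks, the first scan at 4-6 weeks, and the under-6-weeks limit on Type 2a. No cut-off is proposed here. Counting 2a- only from 6 weeks, for example, would leave the dependence on scan date in place and could exclude an infant called 2a- and treated earlier.

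The cost is protocol wording. No new data, visits or sample size are needed, and no treatment rule is proposed.
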